1.4 History of amendments

EOCRC1-22 protocol version (date)	Key points of protocol version (only substantial changes listed)
Version 1.0 (2022-MAR-28)	For authority submissions
Version 2.0 (2002-JUL-04)	Updated version following IND review by the FDA

2 RATIONALE

2.1 Rationale for the study

Detectable ctDNA after completion of curative therapies can identify patients with high-risk CRC, but still with a very limited tumor burden. Thus, a minimal residual disease (MRD) setting which can be assumed to be advantageous, especially for some treatment options, e.g. immunotherapy approaches. The MRD setting has, since a longer time, been targeted for curative treatment approaches with some success in hematological malignancies.

Patients with ctDNA defined MRD of CRC after completion of curative therapies are highly likely to recur with overt metastatic disease (positive predictive value of ctDNA is approximately 100% by 3 years).

Patients with ctDNA positive testing have disease shedding tumor DNA into the circulation, which at early stages might represent radiographically undetectable micrometastatic disease.

The lead-time of ctDNA positivity to radiographic recurrence is up to 6-9 months that provides a window for early initiation of systemic therapy towards eradication of micrometastatic disease [22]. Clearance of ctDNA may be used as a surrogate endpoint under the assumption that this is necessary (albeit insufficient as of now) for eventual cure [93, 94].

We hypothesize that EO2040 in combination with nivolumab in patients with ctDNA-defined MRD will eradicate micrometastatic disease resulting in ctDNA clearance and improvement in disease free survival (DFS) compared to MRD-positive historical controls. The background for this hypothesis has been outlined in [Section 1.3](#).

Patients with CRC being treated with curative intent, dependent on institution and country of treatment, might routinely have ctDNA analysis at key time points including at diagnosis, completion of each line of therapy, post-surgery, post-adjuvant therapy, and during surveillance. Screening for ctDNA-defined MRD is assumed to be done as standard-of-care per current practices.

3 STUDY OBJECTIVES AND ENDPOINTS

3.1 Objectives

3.1.1 Primary objective

- The primary objective of this trial is to assess the 6-month ctDNA clearance rate at therapy with EO2040 in combination with nivolumab, in patients with ctDNA-defined MRD of stage II-IV colorectal cancer after completion of curative therapy.

and in sequence, provided the first objective has a positive outcome per [Section 9](#):

- The primary objective is, to assess the 6-month ctDNA clearance rate at therapy with EO2040 monotherapy, in patients with ctDNA-defined MRD of stage II-IV colorectal cancer after completion of curative therapy.
 - *In case the first objective does not have a positive outcome per [Section 9](#), a protocol amendment to adjust the second part of the primary objective to utilize an alternative therapeutic vaccine than EO2040 will be considered.*

ctDNA clearance is utilized as a surrogate endpoint for eventual cure, and thereby prolongation of disease-free survival (DFS) for patients achieving clearance.

Note, clearance of ctDNA is characterized by the disappearance of all somatic mutations identified in the blood, as well as no appearance of any additional new somatic mutations, and radiographic investigation(s) showing no evidence of colorectal cancer (see [Section 7.8](#)).

3.1.2 Secondary objectives

To assess the following items at therapy with EO2040 in combination with nivolumab, and when applicable EO2040 monotherapy, in patients with ctDNA-defined MRD of stage II-IV colorectal cancer after completion of curative therapy:

1. safety and tolerability of study treatments,
2. the 3-month ctDNA clearance rate,
3. progression of colorectal cancer and death as disease-free survival (DFS),
4. overall survival (OS),
5. survival at 36 months after start of study therapy, and
6. induction/expansion of T cells specific for EO2040, the components of EO2040, and the targeted nominal TAAs (BIRC5 and FOXM1).

3.1.3 Exploratory objectives

1. [REDACTED]
2. [REDACTED]

3. To assess correlations between immunogenicity of EO2040, the components of EO2040, and the targeted nominal TAAs (BIRC5 and FOXM1) and efficacy, and safety, outcome parameters.

4. [REDACTED]
- [REDACTED]

3.2 Endpoints

3.2.1 Primary endpoint

Response to therapy will be measured with a standard-of-care, CLIA certified ctDNA assay, or similar certification outside of the USA, at the evaluation times specified in [Section 7.1](#).

Identification of somatic mutations in the blood will be confirmed by sequencing of the resected tumor using a CLIA-certified next-generation sequencing panel. Clearance of ctDNA will be characterized by the disappearance of all somatic mutations identified in the blood, as well as no appearance of any additional new somatic mutations.

The primary endpoint is response to treatment at 6 months (see [Section 3.1.1](#)), which is defined as having clearance of ctDNA, AND not having any radiographic evidence of recurrence at 6 months (see also [Section 7.8](#) for rules of assessment of an individual patient best overall response).

[REDACTED]

[REDACTED]

[REDACTED]

3.2.2 Secondary endpoints

1. The safety and tolerability of study treatments will be determined by a descriptive medical assessment of the combined profile of incidences of adverse events (AEs), treatment-emergent AEs (TEAEs), serious AEs (SAEs), deaths, reasons for treatment discontinuation/delays, and laboratory abnormalities using the NCI-CTCAE v5.0 grading system [100]. See further [Section 7.7](#).
2. Response to therapy at 3 months, defined as clearance of ctDNA, AND no radiographic evidence of recurrence (determination method will be the same as for the primary endpoint; see [Section 3.2.1](#)).

- 3. Disease-free survival (DFS) defined as the time from start of study treatment to the date of first documented CRC recurrence or death due to any cause, whichever occurs first. Patients alive without recurrence will be censored at the date of last follow-up time. Recurrence is defined by the appearance of one or more new CRC lesions on imaging and/or other clinical evaluation such as endoscopy.
- 4. Overall survival (OS), measured as the time from start of study treatment until death from any cause. Patients alive will be censored at the last time documented to be alive.
- 5. Survival at 36 months after start of study treatment, estimated via Kaplan-Meier estimates.
- 6. Immunogenicity and cross reactivity: immunogenicity determined as expansion of specific T cells comparing samples taken at baseline versus on treatment in an individual patient

[REDACTED]

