ctDNA is composed of short fragments of tumor-derived DNA (roughly 130-150 base pairs) that are released by cancer cells into the circulation via apoptosis, necrosis, or secretion [20]. Detectable ctDNA after completion of curative therapies has nearly 100% positive predictive value for radiographic recurrence. Multiple studies demonstrate that the presence of ctDNA likely reflects radiographically unseen micrometastases, or minimal residual disease (MRD), which is predictive of recurrence and a useful screening tool for high-risk patients [21].

The lead-time of ctDNA positivity to radiographic recurrence is up to 9 months in early-stage disease, which provides a window for evaluation of novel therapies in a setting for which there are no current standard-of-care guidelines [22].

Clearance of ctDNA may be used as an endpoint in early-stage studies to stratify patients for more definitive trials and promote drug development in this space. The improved detection of ctDNA has provided a unique opportunity to use a noninvasive approach in order to explore therapeutic options and to potentially eradicate micrometastatic disease in high-risk patients.

1.2.3

1.3 EO2040 a microbiome-derived therapeutic vaccine for treatment of minimal residual disease of colorectal cancer

Extensive pre-clinical studies have been conducted to characterize the microbiome-derived mimicry therapeutic vaccine concept (**Figure 2**), currently including two multi-peptide compounds in clinical trials (EO2401 in glioblastoma, adrenocortical carcinoma, and malignant pheochromocytoma/paraganglioma, and EO2463 in follicular and marginal zone lymphoma), and one compound in preparation for clinical trials (EO4010; targeted for multiple solid tumor types, including breast, colorectal and non-small cell lung cancer).

EO2040, the compound to be used in the current trial is a derivative of the compound EO2401. EO2040 include the same components as EO2401, except the microbiome derived peptide EO2316, mimicking an epitope on the TAA interleukin 13 receptor alpha-2 (IL-13R α 2). The reason to exclude peptide EO2316 from compound EO2040 is that IL-13R α 2 currently does not have a rationale to be used when colorectal cancer is targeted, i.e. expression levels as known today are not high enough.

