6.7.3 Prohibited medications and other therapies

The use of systemic corticosteroids and other immunosuppressants should be avoided because of their potential interference with the pharmacodynamics activity of the study treatment. However, in some cases, systemic corticosteroids cannot be avoided; guidance regarding steroid use for patients participating in the trial is therefore outlined in [Section 6.7.2](#).

The use of live or attenuated vaccine therapy for prevention of infectious diseases during treatment with study medication and for at least 3 months after end of treatment with study medication should be avoided. If there is no alternative, to live or attenuated, vaccine available, and it is considered of utmost importance for the individual patient to receive the

vaccine, an individual benefit/risk assessment should be made regarding the duration of "wash-out" period necessary after termination of study treatment, and study treatment should be stopped as applicable.

Patients should be discouraged from taking medications, including herbal remedies, with immunostimulatory properties, or known to potentially interfere with major organ function, during trial participation. If needed, any such possible therapy should be discussed between the treating physician and the Medical Monitor of the Sponsor.

During trial participation patients should not receive any other anti-CRC treatment than the specified trial treatments, and treatments outlined in [Section 6.7.2](#).

If any other anti-CRC treatment, or procedure, would be considered for start in an individual patient, it is the duty of the Investigator to discuss the consideration with the Medical Monitor of the Sponsor for a decision on how to handle continued trial specific treatment and trial participation.

Start of non-trial systemic anti-CRC treatments would lead to censoring of the patient for relapse related endpoints at the time of start of the therapy; or assessment of the patient as having relapsed disease if relevant criteria would be fulfilled.

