7.6 Visits during post-treatment follow-up

7.6.1 *Post-treatment visits before determination of relapsed disease*

Patients who have permanently stopped all study treatment without having had confirmation of relapsed disease will be followed

At these timepoints the following is to be done (see also **Table 8**):

- CT scanning is to be done every 3-6 months per standard of care for the patient's stage of CRC disease (See [Section 1.1](#) regarding recommendations for surveillance after curative treatments); collection of information from a protocol perspective should be done until scan documented relapse of disease (or until other

anti-cancer treatment would be started before confirmed progressive disease), or for a maximum of 3 years from first study treatment in the individual patient,

- [REDACTED] continue ctDNA testing per local standard of care; collection of information from a protocol perspective should be done until scan documented relapse of disease (or until other anti-cancer treatment would be started before confirmed progressive disease), or for a maximum of 3 years from first study treatment,
- [REDACTED]
- [REDACTED]
- [REDACTED]
- documentation of safety; [REDACTED]
- if applicable, for female patients of childbearing potential, a serum pregnancy test will continue to be done on a monthly basis until 6 months after study treatments have been stopped, if not a new anti-tumor treatment has been initiated earlier in which case the study related testing will be terminated at the time of start of new anti-tumor treatment, and
- if applicable, collection of information regarding further anti-cancer treatments.

[REDACTED]

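### Do the protocol's two censoring rules for disease-free survival inflate the DFS result?

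*Protocol*

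**What the plan says.** **Protocol 3.2.2** opens the endpoint with "Disease-free survival (DFS) defined as the time from start of study treatment to the date of first documented CRC recurrence or death due to any", that is, death whatever its reason. On censoring it states "Patients alive without recurrence will be censored at the date of last follow-up time". It does not say whether follow-up here means the last disease assessment or the last contact. For overall survival the same section censors at the last time the patient was documented to be alive, which is different wording.

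**Protocol 6.7.3** says that the start of non-trial systemic anti-CRC treatment "would lead to censoring of the patient for relapse related endpoints at the time of start of the therapy". It then gives an alternative: "or assessment of the patient as having relapsed disease if relevant criteria would be fulfilled".

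**Protocol 7.6.1** collects scan results up to documented relapse "or until other anti-cancer treatment would be started before confirmed progressive disease", with an upper limit of 3 years counted from the patient's first dose. The ctDNA bullet carries the same stopping clause. Further anti-cancer treatments are still recorded, and Protocol 4.2 keeps patients in study follow-up for up to 3 years from start of study treatment.

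**SAP 4.2.2** repeats the 3.2.2 definition and does not mention 6.7.3. It belongs to SAP section 4, which is an overview of the protocol. SAP 3.1 and 5.4 state that no formal analysis will be done because the study is planned to end with one treated patient. SAP 7.1.1 and 11.1 state that no tables or figures will be produced.

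**The concern.** DFS is a relapse-related endpoint, so 3.2.2 and 6.7.3 both apply to a patient who starts other therapy before a documented recurrence, and they can give different censoring dates. The stop on scan collection makes this more than a matter of wording. If last follow-up means last contact, a patient whose scans are no longer collected goes on gaining recurrence-free time.

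The censoring may also be informative. The trial is open-label, ctDNA testing continues under local practice, and Protocol 1.2.2 states: "Detectable ctDNA after completion of curative therapies has nearly 100% positive predictive value for radiographic recurrence". Patients who switch early are plausibly those closest to recurrence, in which case censoring them at therapy start also flatters DFS.

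The stake would be real in a completed trial. Clearance is used as a surrogate for cure and longer DFS (Protocol 3.1.1), and Protocol 2.1 hypothesises better DFS than in historical controls, with no concurrent arm to share the bias.

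**Working it through.** The readable documents give no DFS rate, median, event count or power, so there is no stated figure to reproduce. All rates below are assumptions used to show size.

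**1. One patient under each reading.** Suppose other therapy starts at month 8 with no documented recurrence, and the patient is known alive at month 36.

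| Reading | DFS time |
|---|---|
| 3.2.2, last follow-up = last contact | censored at month 36 |
| 3.2.2, last follow-up = last disease assessment | censored at or before month 8, because 7.6.1 stops scan collection there |
| 6.7.3, relapse criteria not met | censored at month 8 |
| 6.7.3, relapse criteria met | event |

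The gap of 36 − 8 = 28 months appears only under the last-contact reading. Under the second reading, 3.2.2 and 6.7.3 nearly agree.

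**2. A severe case.** Assume exponential time to recurrence with median 9 months, a fraction f = 0.30 starting therapy exactly 1 month before recurrence would be documented, and no deaths.

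- True 12-month DFS: 2^(−12/9) = 0.397.
- Probability of no recurrence in month 1: 2^(−1/9) = 0.926. A patient who recurs in month 1 cannot switch first and counts as an event.
- Last contact: 0.70 × 0.397 + 0.30 × 0.926 = 0.278 + 0.278 = 0.556 (simulated 0.555).
- Censoring at therapy start: after month 1 the observed hazard is 0.70/(0.70 + 0.30 × 0.926) = 0.716 of the true hazard ln 2/9 = 0.0770 per month. DFS at 12 months is then about 0.925 × exp(−0.716 × 0.0770 × 11) = 0.504 (simulated 0.504). The factor 0.925 is DFS at month 1, when hardly anyone has yet been censored.

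With f = 0.15 the simulated values are 0.396 true, 0.475 last contact and 0.446 at therapy start.

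**3. A wider range.** Simulation of 400,000 patients per scenario. Assumptions: median time to recurrence 9, 12 or 18 months; 10%, 20% or 40% of patients due to start therapy at 3 to 9 months if still recurrence-free; recurrence hazard in those patients 1, 2 or 3 times that of the others; recurrence unseen after the switch; deaths counted under the last-contact rule, with median 30 months from recurrence to death; 36 months of follow-up. DFS at 24 months:

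| Scenario (median, share, hazard ratio) | True | Last contact | Therapy start |
|---|---|---|---|
| 12 months, 20%, 1 | 24.9% | 32.2% | 24.9% |
| 12 months, 20%, 2 | 21.2% | 28.0% | 23.5% |
| 9 months, 10%, 3 (smallest last-contact bias) | 14.3% | 16.1% | 14.9% |
| 9 months, 40%, 1 (largest last-contact bias, about level with 18 months, 40%, 2) | 15.8% | 30.7% | 15.8% |
| 18 months, 40%, 3 (largest therapy-start bias) | 26.3% | 40.0% | 33.7% |

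The last-contact rule overstates DFS by 16.1 − 14.3 = 1.8 to 30.7 − 15.8 = 14.9 points. Censoring at therapy start overstates it by 0 to 33.7 − 26.3 = 7.4 points, and is unbiased when switching is unrelated to recurrence risk.

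**4. What the SAP will compute.** SAP 7.1.2 lists the CRF data as documented, together with the variables derived in SAP section 6. The readable part of section 6 defines baseline, change from baseline, study day, duration and visit labels, and no DFS time. With one treated patient there is no Kaplan-Meier estimate, no median and no comparison with historical controls. The choice of censoring rule therefore enters no planned output.

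**The case for a change.** The best case for a change is that the conflict stands in current text, the remedy is cheap, and choosing a censoring date would not be enough. In the severe case above, censoring at the last scan with 3-monthly scans still gives about 49% at 12 months against 40% true, so 7.6.1 would have to change as well.

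Part of this stands. The sections are not reconciled, the follow-up date is undefined, and a last-contact reading would bias DFS upward in any real analysis.

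The rest is weaker.

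- The last-contact reading is the least natural one, since 3.2.2 uses different words for overall survival. The sections fit together if 3.2.2 is the general rule, 6.7.3 the specific rule for new therapy, and 7.6.1 the matching data collection.
- The severe case borrows 9 months from a lead time between ctDNA positivity and radiographic recurrence, described as up to 9 months in Protocol 1.2.2 and up to 6-9 months in 2.1. That is not a median from start of study treatment. The 30% is not in the documents. Adding deaths at a median of 30 months after recurrence lowers the last-contact figure from 55% to 53%.
- Following patients through new therapy, instead of censoring them, changes the estimand by including the effect of off-protocol treatment. Statisticians differ on that choice, and the protocol has made one.
- Parts of Protocol 9.2 are blacked out, so further DFS handling may be specified there.

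**Conclusion.** No change is needed, because it would gain nothing. The inconsistency is genuine but alters no reported number: the SAP plans only listings for one treated patient. The scan, treatment and survival dates recorded for that patient are to be listed as documented, so a reader can see the course without any censoring rule.

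The 2 to 15 points for last contact and 0 to 7 points for therapy start describe a DFS analysis that will not be run, under assumed recurrence and switching rates. The conclusion rests on the SAP standing as final. If the protocol text were reused for a trial that estimates DFS, the censoring date should be defined and 3.2.2 tied to both branches of 6.7.3.

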3.2.3 Exploratory endpoints

[REDACTED]

[REDACTED]

- 3. Correlations between immunogenicity [REDACTED] of EO2317, EO2318, and UCP2 and clinical efficacy (per primary and secondary efficacy endpoints) and safety (TEAEs of defined specificities and grades) outcome parameters. Cross reactivities shown for the TAAs BIRC5/survivin, and FOXM1 will also be explored in the same way.

[REDACTED]

[REDACTED]

[REDACTED]

■ [REDACTED]

[REDACTED]

[REDACTED]

[REDACTED]

[REDACTED]

■ [REDACTED]

[REDACTED]

[REDACTED]

[REDACTED]

[REDACTED]

[REDACTED]

[REDACTED]

■ [REDACTED]

[figure not shown]
4 STUDY DESIGN

4.1 Overall trial design and timelines

The trial is a multi-center, open-label, non-comparative, two sequential cohort, phase 2 trial, to investigate as the first cohort efficacy of the microbiome-derived therapeutic vaccine EO2040 in combination with nivolumab in patients with stage II-IV colorectal cancer with ctDNA defined MRD after completion of curative therapy. Assuming a positive outcome of the first cohort, a second cohort assessing efficacy of EO2040 monotherapy, with the option of addition of nivolumab after 3 months in case of no ctDNA clearance, is planned.

The objectives of the trial are outlined in [Section 3.1](#).

[figure not shown]
The study is assumed to recruit a total of 17 patients in Cohort 1, and if cohort 1 has a positive outcome (see [Section 9](#)), a total of 17 patients will also be recruited to Cohort 2A.

For details regarding sample size determination and statistical analyses see [Section 9](#).

Figure 15 gives a schematic overview of the trial design, and an overview of the treatment schedule is displayed in **Figure 16** (for further specifics see the Study Schedule in [Section 7.1](#)).

Figure 15 : EOCRC1-22 Overview trial design

4.2 General trial design

There will be a 2-stage consent procedure for the trial, including a first consent for basic disease, age information, and HLA-typing (or the use of already available information in the patients' file; such information even if based on testing before the screening period is acceptable) since a large proportion of the patients (approximately half of the patients) will not match the HLA-A2 prerequisite to receive the HLA-A2 specific EO2040 immunization compound. The reason for the initial minimized consent (related to the procedure of HLA-testing, and before testing also establishing based on available information that the patient is eligible in relation to CRC type, prior therapy, and has an age ≥ 18 years) is to spare the necessity of all other testing for possible enrollment in the trial for patients who are not known to be HLA-A2 positive.

The second stage of the consent procedure will be related to treatment, and follow-up aspects of the trial procedures.

[REDACTED]

Study treatments will be administered until study treatment termination criteria as outlined in [Section 5.3.3](#) are fulfilled, e.g. reaching maximum study treatment period (6 months), unacceptable toxicity, or relapsing disease. At the time of stopping study treatment, appropriate other treatment will be advised by the treating physician on an individual patient basis. The patient should continue, even if study treatment is stopped, study follow-up measures for as long as the individual patient consent for follow-up is not withdrawn, the site is open, and the study not terminated per plan, or early, but for a maximum length of 3 years after start of study treatment.

All assessments of possible relapse in the trial will be determined at the sites by the principal investigators, or designees, according to the standard clinical criteria used at the site.

Of note, there is no current knowledge publicly available regarding the potential of pseudoprogression at immunotherapy in patients with ctDNA defined MRD of CRC. Thus, at scanning, especially at the 3-month study timepoint, if a relapse is indicated by scanning it is recommended to, if at all possible, also document the relapse with histology or cytology.

